5.7.2.5. Iron Parameter Related Analysis

Iron metabolism parameters including serum iron, total iron binding capacity (TIBC), transferrin, soluble transferrin receptor, ferritin, non-transferrin bound iron (NTBI), and hepcidin will be taken at Screening, Cycle 1 Day 1, Day 1 and Day 8 of Cycle 2, Day 1 of Cycle 3, 4, and 5, EOT, PTFU and EOS visits. Descriptive statistics of observed values, absolute and percentage change from baseline values at each post baseline visit will be presented by dose cohort.

Shift analyses will also be performed to summarize serum ferritin EOT change from baseline. Serum ferritin will be grouped into three categories: < 300 , ≥ 300 for males; < 150 , ≥ 150 for females and ≤ 1000 , ≥ 1000 ($\mu\text{g/L}$).

Plots of iron parameters for both mean observed values and mean change from baseline over time will be presented by dose cohort.

5.7.2.6. Erythropoietin Parameters

Blood samples relating to erythropoietin parameters including serum erythropoietin levels, reticulocytes and nucleated RBCs will be taken at Screening, Day 1, 8, and 15 of Cycles 1, Day 1 of Cycle 2 and 4, EOT, PTFU and EOS visits. Descriptive statistics of observed values, absolute and percentage change from baseline values at each post baseline visit will be presented by dose cohort. Plots of erythropoietin parameters for both mean observed values and mean percentage change from baseline over time will be presented by dose cohort.

5.7.2.7. Bone Metabolism Parameters

Bone metabolism parameters including bone specific alkaline phosphatase (BSAP) and C-telopeptide of type I collagen (CTX) will be taken at Cycle 1 Day 1, Cycle 4 Day 1, and EOT visits. Descriptive statistics of observed values, absolute and percentage change from baseline values at each post baseline visit will be presented by dose cohort.

5.7.2.8. Hemolysis Parameters

Hemolysis parameters include direct bilirubin, total bilirubin, and lactate dehydrogenase (LDH). Descriptive statistics of observed values, absolute and percentage change from baseline values at each post baseline visit will be presented by dose cohort. Plots of

hemolysis parameters for both mean observed values and mean percentage change from baseline over time will be presented by dose cohort.

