 **Bone marrow aspirate/biopsy** including cytogenetics at screening must be performed  $\leq$  3 months prior to C1D1 for evaluation of patient eligibility and other PD biomarkers to be determined (e.g., GDF15, GDF8, and GDF11).

- For all patients, at the end of treatment visit, a bone marrow aspirate must be performed (a bone marrow biopsy is optional).
- Dose escalation cohorts and expansion cohort 1 patients only: a bone marrow aspirate must be performed within 21 days after C3D1 (a bone marrow biopsy is not required). Note: A bone marrow aspirate is not required within 21 days after C3D1 for expansion cohort 2 patients.
- Dose escalation cohorts and expansion cohort 1 patients only: If hemoglobin increases  $\geq$  2 g/dL, an optional bone marrow aspirate can be performed within 7 days of the result.

 **Iron Studies:** Serum iron, TIBC, transferrin, soluble transferrin receptor, NTBI, ferritin.

 **Hematology:** RBC, WBC with differential, hemoglobin, hematocrit, nRBC, reticulocyte count, platelet count, MCV, MCH, MCHC, and RDW. On dosing days, hemoglobin values are to be drawn and resulted (up to 1 day) prior to dosing (see [Section 10.8.1](#), Patient Dose Modification Rules). Historical hemoglobin data will be collected for 24 weeks, where available, prior to C1D1. During the screening period, hemoglobin will be measured twice; one measure performed within one day prior to Cycle 1 Day 1 and the other performed 7-28 days prior to Cycle 1 Day 1. Neither hemoglobin measure should be influenced by transfusion within 7 days of measurement.

 **Chemistry:** Sodium, potassium, AST, ALT, lactate dehydrogenase (LDH), total bilirubin, direct bilirubin, alkaline phosphatase, blood urea nitrogen (BUN)/urea, creatinine, GGT, calcium, phosphorus, glucose, amylase, lipase, total protein, albumin, and uric acid.

 **Urinalysis by dipstick analysis (local lab):** pH, specific gravity, protein, glucose, ketones, blood, leukocyte esterase, and nitrite, with microscopic examination if indicated. **Urine Chemistry (central lab):** Microalbumin and creatinine.

 **PD Biomarkers:** Hepcidin, GDF15, GDF8, GDF11, and others to be determined.

 **Bone Biomarkers:** BSAP and CTX. Not required for expansion cohort 2 patients.

 **Pregnancy test:** (urine or serum) is required for female patients of child bearing potential at screening and prior to each dose of ACE-536.

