5.8.3. Laboratory Evaluations

Results from the following laboratory parameters, recorded at their respective time points will be summarized by dose cohort and time point:

Hematology: (Screening, Days 1, 8 and 15 of each cycle, End of Treatment, Post Treatment Follow Up and End of Study).

RBC, WBC with differential, hemoglobin, hematocrit, haptoglobin (optional), reticulocyte count, platelet count, MCV, MCH, MCHC, RDW, and nRBCs

Chemistry: (Screening, Days 1 and 15 of Cycle 1, and Days 1 and 8 of each subsequent cycle, End of Treatment and End of Study).

Sodium, potassium, chloride, carbon dioxide/bicarbonate (optional), AST, ALT, lactate dehydrogenase (LDH), total bilirubin, indirect bilirubin, alkaline phosphatase, blood urea nitrogen (BUN)/urea, creatinine, GGT, calcium, phosphorus, glucose, amylase, lipase, total protein, albumin, and uric acid

Urine: (Day 1 of Cycles 1, 2 and 4, End of Treatment and End of Study).

PH, specific gravity, protein, glucose, ketones, blood, leukocyte esterase, and nitrite, with microscopic examination if indicated; Microalbumin and creatinine

Urine Chemistry: (Day 1 of Cycles 1, 2 and 4, End of Treatment and End of Study).

Microalbumin and creatinine will be performed by the central lab; individual and mean UACRs over time (for the ITT group) will be computed

Categorical and numeric variables will be presented separately.

Actual values and changes in hematology and biochemistry laboratory values from baseline will be summarize by dose cohort and by time point.

Shift tables for the hematology and biochemistry laboratory parameters comparing values above, within and below the normal reference range at baseline to the end of treatment visit will be presented using standard reference ranges.

Peripheral blood smears are taken at Screening, Day 1 of Cycles 1, 2, and 5 and at the end of treatment visit. These data will be listed only.

All laboratory values will be listed for all patients.

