- Dose escalation cohorts and expansion cohort 1 patients only: a bone marrow aspirate must be performed within 21 days after C3D1 (a bone marrow biopsy is not required). Note: A bone marrow aspirate is not required within 21 days after C3D1 for expansion cohort 2 or 3 patients.
- Dose escalation cohorts and expansion cohort 1 patients only: If hemoglobin increases \geq 2 g/dL, an optional bone marrow aspirate can be performed within 7 days of the result.

⁴ **Iron Studies:** Serum iron, TIBC, transferrin, soluble transferrin receptor, NTBI, ferritin.

⁵ **Hematology:** RBC, WBC with differential, hemoglobin, hematocrit, nRBC, reticulocyte count, platelet count, peripheral blasts (on dosing days only: C1D1, C2D1, C3D1, C4D1, C5D1), MCV, MCH, MCHC, and RDW. On dosing days, hemoglobin values are to be drawn and resulted (up to 1 day) prior to dosing (see Section **Error! Reference source not found.**, Patient Dose Modification Rules). Historical hemoglobin data will be collected for 24 weeks, where available, prior to C1D1. During the screening period, hemoglobin will be measured twice; one measure performed within one day prior to Cycle 1 Day 1 and the other performed 7-28 days prior to Cycle 1 Day 1. Neither hemoglobin measure should be influenced by transfusion within 7 days of measurement.

⁶ **Chemistry:** Sodium, potassium, AST, ALT, lactate dehydrogenase (LDH), total bilirubin, direct bilirubin, alkaline phosphatase, blood urea nitrogen (BUN)/urea, creatinine, GGT, calcium, phosphorus, glucose, amylase, lipase, total protein, albumin, and uric acid.

⁷ **Urinalysis by dipstick analysis (local lab):** pH, specific gravity, protein, glucose, ketones, blood, leukocyte esterase, and nitrite, with microscopic examination if indicated. **Urine Chemistry (central lab):** Microalbumin and creatinine.

⁸ **PD Biomarkers:** Hepcidin, GDF15, GDF8, GDF11, and others to be determined.

⁹ **Bone Biomarkers:** BSAP and CTX. Not required for expansion cohort 2 or 3 patients.

¹⁰ **Pregnancy test:** (urine or serum) is required for female patients of child bearing potential at screening and prior to each dose of ACE-536.

¹¹ **Transfusion history** will be collected for 24 weeks, where available, prior to C1D1.

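### The SAP's hemolysis panel includes direct bilirubin but omits the indirect fraction, and its bilirubin lists disagree with no derivation rule to connect them

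*SAP*

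**What the plan says.** SAP 5.7.2.8, placed among the secondary efficacy endpoints, defines the panel: "Hemolysis parameters include direct bilirubin, total bilirubin, and lactate dehydrogenase (LDH". For each parameter it plans tables ("Descriptive statistics of observed values, absolute and percentage change from baseline values at each post baseline visit will be presented by dose cohort") and plots of "hemolysis parameters for both mean observed values and mean percentage change from baseline over time will be presented by dose cohort". Indirect bilirubin is not mentioned there.

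SAP 5.8.3, which governs the safety laboratory summaries, lists "lactate dehydrogenase (LDH), total bilirubin, indirect bilirubin, alkaline phosphatase". It names indirect bilirubin and leaves direct out.

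The collection lists agree with each other and differ from 5.8.3. Footnote 6 of the protocol's Schedule of Events reads "lactate dehydrogenase (LDH), total bilirubin, direct bilirubin, alkaline phosphatase", protocol 11.2 names the same two fractions, and footnote 6 of SAP Appendix 2 has "total bilirubin, direct bilirubin, alkaline phosphatase".

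Neither document says how indirect bilirubin is obtained. SAP 5.15, which lists the major changes from the protocol, does not mention bilirubin.

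**The concern.** Breakdown of red cells, in the circulation or in the marrow, adds to unconjugated (indirect) bilirubin. The direct fraction has already been conjugated by the liver and mainly follows hepatobiliary excretion. This is general physiology and the documents do not state it. It matters for this trial because protocol 7.1 attributes the anemia of MDS to ineffective erythropoiesis with cell death in the marrow, and protocol section 7 describes the drug as acting on late red-cell maturation. A change in red-cell turnover is thus a natural question for this panel.

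As written, the section on red-cell breakdown carries the hepatobiliary fraction and leaves out the one of interest, while the general chemistry section does the reverse. Two things are at stake. A change confined to the indirect fraction would be absent from one of the three hemolysis parameters and weakened in another. A change confined to the direct fraction would appear in tables and plots labelled as hemolysis. In addition, a programmer working from the SAP cannot tell whether indirect bilirubin is to be computed, read from laboratory data, or ignored.

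**Working it through.** The documents give no bilirubin values and no target figure for this panel, so there is no stated number to reproduce. The check compares the lists and then uses illustrative values.

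**Step 1: the lists side by side**

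| Place | Total | Direct | Indirect |
|---|---|---|---|
| Protocol Schedule of Events, footnote 6 | yes | yes | no |
| Protocol 11.2 | yes | yes | no |
| SAP Appendix 2, footnote 6 | yes | yes | no |
| SAP 5.7.2.8 (hemolysis) | yes | yes | no |
| SAP 5.8.3 (safety chemistry) | yes | no | yes |

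**Step 2: availability of the inputs.** SAP 5.8.3 gives the chemistry visits as "Screening, Days 1 and 15 of Cycle 1, and Days 1 and 8 of each subsequent cycle, End of Treatment and End of Study". That is 1 (screening) + 2 (Cycle 1) + 2 x 4 (Cycles 2 to 5) + 2 (EOT and EOS) = 13 time points. Total and direct belong to one chemistry panel, so indirect = total - direct can be formed at each of them.

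**Step 3: dilution.** Assume that direct is a share d of total, with d from 10% to 30%, and that indirect falls by 30% with direct unchanged. Then change in total = -30% x (1 - d).

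- d = 10%: -30% x 0.90 = -27%
- d = 30%: -30% x 0.70 = -21%
- Direct: 0% in both cases
- Indirect: -30% in both cases

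Total bilirubin keeps the direction and 70% to 90% of the size.

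**Step 4: mislabelling.** Assumed values in mg/dL:

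- (a) Total 1.0 to 1.6, direct fixed at 0.3. Direct 0%, total +60%, indirect 0.7 to 1.3, that is 1.3/0.7 - 1 = +85.7%.
- (b) Total 1.0 to 1.3, direct 0.3 to 0.6. Direct +100%, total +30%, indirect 0.7 to 0.7, that is 0%.

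In (b) the hemolysis section would show direct bilirubin doubling although the indirect fraction has not moved.

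**Step 5: can indirect be recovered from the planned output?** Take two assumed patients, both with direct unchanged. Patient 1 has total 1.0 to 1.6 with direct 0.3. Patient 2 has total 2.0 to 2.4 with direct 0.4.

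- Mean absolute change: total (0.6 + 0.4)/2 = 0.5, direct 0.0, indirect 0.5. These subtract, provided the same patients contribute.
- Mean percentage change: total (60% + 20%)/2 = 40.0%, direct 0.0%. Indirect is 0.7 to 1.3 (+85.7%) and 1.6 to 2.0 (+25.0%), mean 55.4%. Subtracting the first two gives 40.0%, not 55.4%.

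The percentage-change tables and plots therefore cannot supply the indirect result. It has to be derived per patient and visit before summarising.

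**The case against.** The strongest reply is that the panel still works. Total bilirubin contains the indirect fraction, LDH stands beside it, and a reader who sees total move while direct stays flat can place the change in the indirect fraction. Direct bilirubin is useful for exactly that purpose: in example (b) of the working, direct at +100% against total at +30% points away from hemolysis. Mean absolute changes, which 5.7.2.8 also plans, give the indirect change by subtraction when the same patients contribute. All of this stands. It is why the panel is not void and why direct should stay as a comparator. It does not justify leaving out the specific fraction or presenting direct as a hemolysis measure, and it does not help with the percentage changes.

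A second reply is that SAP 5.8.3 already plans actual values and changes from baseline for indirect bilirubin by dose cohort and time point, with shift tables to end of treatment. That may be so, but without a derivation rule, and with indirect missing from every supplied collection list, the entry can be read either as an unwritten derivation or as a slip.

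A reader might infer from the lists that 5.8.3 names an analyte that is not collected. The documents do not prove that. The SAP states that it follows protocol amendment 06, and the supplied protocol does not appear to be that version: it has no expansion cohort 3 and plans up to 128 patients against 153 in the SAP. SAP 5.8.3 also lists chloride, optional bicarbonate and optional haptoglobin, none of which is in the supplied protocol's laboratory lists or in Appendix 2. The safe statement is that indirect bilirubin is in no supplied collection list.

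Finally, the stakes are low. Hemolysis is not named in the objectives of either document or in the protocol's secondary analyses, and SAP 5.2 makes every summary descriptive. This limits the severity but does not resolve the inconsistency.

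**Conclusion.** The point holds as a minor one. The SAP's hemolysis section omits the bilirubin fraction most closely tied to red-cell breakdown, its two analysis sections name different fractions, and nothing connects them. The effect is one diluted and partly mislabelled descriptive panel, with no bearing on mHI-E, the sample size or any decision rule.

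A reader might go further and infer that the analysis would give the wrong answer about red-cell turnover. That is not supported: under the assumptions used here, total bilirubin moves in the right direction, and LDH is reported independently of the bilirubin fractions.

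The conclusion rests on general physiology for what each fraction reflects. The sizes rest on an assumed direct share of 10% to 30% and an assumed 30% change, not on trial data. The mismatch between the lists rests on the text alone.

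**What to change.** - **SAP 5.7.2.8:** add indirect bilirubin, derived for each patient and visit as total minus direct from the same sample, as the bilirubin measure of hemolysis alongside total bilirubin and LDH. Compute its absolute and percentage changes from the derived values, not from the summary tables. Keep direct bilirubin only as a labelled hepatobiliary comparator.
- **SAP 5.8.3:** list direct bilirubin as collected and indirect as derived, or as laboratory-reported if amendment 06 collects it.
- **Alignment:** make 5.7.2.8, 5.8.3 and Appendix 2 name the same analytes.

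The cost is one derived variable, its tables and plots, and a few lines of SAP wording. No new samples or visits are needed, and the change can be made before database lock.

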5.7.2.9. Other Analysis

For the following continuous variables, the descriptive statistics including mean, median and range will be presented by dose cohort:

- Maximum reduction in transfusion burden from baseline in HTB patients
- Maximum increase in hemoglobin level from baseline in LTB patients
- Maximum mean change of hemoglobin from baseline during any rolling 8-week in LTB patients
- Maximum percentage decrease in serum ferritin
- Maximum change in absolute reticulocytes
- Change in pre-transfusion hemoglobin levels in high transfusion burden patients
- Frequency of RBC transfusions in high transfusion burden patients
- The proportion of patients with an increase of ≥ 1.0 g/dL from baseline hemoglobin maintained ≥ 8 weeks in LTB patients

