### **9.3.2. Exclusion Criteria**

Eligible patients must not meet **any** of the following criteria.

1. Prior treatment with azacitidine (injectable or oral) or decitabine.
2. Treatment within 28 days prior to Cycle 1 Day 1 with:
  - Erythropoiesis stimulating agent (ESA),
  - Granulocyte colony-stimulating factor (G-CSF) and granulocyte-macrophage colony-stimulating factor (GM-CSF),
  - Lenalidomide.
3. Iron chelation therapy if initiated within 56 days prior to Cycle 1 Day 1.
4. Treatment with another investigational drug or device, or approved therapy for investigational use  $\leq 28$  days prior to Cycle 1 Day 1, or if the half-life of the previous product is known, within 5 times the half-life prior to Cycle 1 Day 1, whichever may be longer.
5. Major surgery within 28 days prior to Cycle 1 Day 1. Patients must have completely recovered from any previous surgery prior to Cycle 1 Day 1.
6. Platelet count  $< 30 \times 10^9/\text{L}$ .
7. Any active infection requiring parenteral antibiotic therapy within 28 days prior to Cycle 1 Day 1 or oral antibiotics within 14 days of Cycle 1 Day 1.
8. History of stroke, deep venous thrombosis (DVT) or arterial embolism within 6 months prior to Cycle 1 Day 1.
9. Known positive for human immunodeficiency virus (HIV), active infectious hepatitis B (HBV) or active infectious hepatitis C (HCV).

10. Any malignancy other than MDS which has not been in remission and/or has required systemic therapy including radiation, chemotherapy, hormonal therapy or surgery, within the last year prior to Cycle 1 Day 1.
11. Uncontrolled hypertension defined as systolic blood pressure (BP)  $\geq 150$  mm Hg or diastolic BP  $\geq 100$  mm Hg.
12. Pregnant or lactating females.
13. History of severe allergic or anaphylactic reactions or hypersensitivity to recombinant proteins or excipients in the investigational drug.
14. Any other condition not specifically noted above which, in the judgment of the investigator, would preclude the patient from participating in the study.
15. Transfusion event within 7 days prior to Cycle 1 Day 1.
16. Prior treatment with sotatercept (ACE-011), or ACE-536.
17. Secondary MDS.

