#### 10.2.1. Other Treatments for MDS

If treatment with azacitidine, decitabine, lenalidomide, ESA, or G-CSF is required during the ACE-536 treatment period, the patient should be discontinued from treatment with study drug and complete the end of treatment visit and enter the follow up period. Iron chelation therapy is allowed unless initiated within 56 days prior to C1D1.

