5. STATISTICAL METHODOLOGY

5.1. Definitions

Low Transfusion Burden (LTB)

LTB patients are defined as those who received < 4 units of RBCs within 8 weeks prior to Cycle 1 Day 1.

High Transfusion Burden (HTB)

HTB patients are defined as those who required ≥ 4 units of RBCs within 8 weeks prior to Cycle 1 Day 1.

Baseline Hemoglobin

Baseline hemoglobin will be an average of hemoglobin measurements within 28 days of Cycle 1 Day 1, excluding measurements within 7 days following RBC transfusion.

Baseline Transfusion Burden

Baseline transfusion burden will be calculated as the total amount of RBC transfusion during the 8 weeks prior to Cycle 1 day 1.

Baseline for Other Parameters

Baseline erythropoietin (EPO) is defined as the maximum test value within 28 days of Cycle 1 Day 1. For all other parameters, baseline is defined as the last observation on or prior to Cycle 1 Day 1.

End of Treatment (EOT)

Procedures and evaluations for the end of treatment visit should be performed on Day 113 (± 7 days) (28 days after the last dose of ACE-536).

Post Treatment Follow-Up (PTFU)

Procedures and evaluations for the post treatment follow-up visit should be performed on Day 141 (± 7 days) (28 days after EOT visit).

End of Study (EOS)

Procedures and evaluations for the end of study visit should be performed on Day 169 (± 7 days) (56 days after the Day 113/EOT visit).

Patients who discontinue treatment early should complete the end of treatment visit at the time of discontinuation and complete the post-treatment follow-up (PTFU) and EOS follow-up visits 28 days (± 7 days) and 56 days (± 7 days) after the EOT visit.

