5.4. Demographic, Baseline Characteristics, and Disease History

The following baseline and demographic characteristics will be summarized by descriptive statistics by dose cohort for ITT population:

- Race, ethnicity, age, sex, height, weight
- Prior MDS Therapies, time from diagnosis; Prior erythropoiesis stimulating agents (ESA); IPSS and IPSS-R risk group; WHO Subtypes
- Baseline ECOG performance status
- Baseline transfusion status (LTB or HTB)
- Baseline hemoglobin for LTB patients only and baseline transfusion burden for HTB patients only.
- Baseline transfusion burden for patients with 2 units or more baseline transfusion.
- Baseline erythropoietin (EPO) and baseline serum ferritin
- RS status and SF3B1 mutation status; any splicing factor (yes or no)
- Baseline bone marrow blasts
- Baseline iron chelation therapy

Demographic and baseline data, medical history, and disease history data will also be listed for each patient.

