5.7. Efficacy Analyses

The analyses for all efficacy endpoints will be performed using the ITT population.

All efficacy summaries will be presented by dose cohort for LTB and HTB patients separately. No formal hypothesis testing is planned. In addition, summaries will also be provided for the following group of patients:

- All patients in the ITT population
- Lower dose group includes patients on 0.125, 0.25 and 0.5 mg/kg dose cohorts
- Higher dose group includes patients on 0.75 mg/kg and above

- Patients in the expansion cohorts 1, 2A, 2B, and 3
- Patients in 0.125 to 0.50 mg/kg dose cohorts, and
- Patients in 0.75 to 1.75 mg/kg dose cohorts.

Efficacy Results will also be summarized with the following groups:

- All RS+ patients
- All RS- patients
- RS+ patients in the high dose (≥ 0.75 mg/kg) cohorts, and
- RS- patients in the high dose (≥ 0.75 mg/kg) cohorts.

In general, below rules apply to the derivations of efficacy endpoints related to hemoglobin and RBC transfusion data unless specified otherwise:

- Hemoglobin measurements within 7 days following RBC transfusion will be excluded from efficacy analysis
- For each patient, all efficacy endpoints will be derived based on the last dose + 56 days or the last date from transfusion record data, whichever is earlier.

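### Ferritin summaries are not split by iron chelation, and the maximum percentage decrease shows a fall even when ferritin has not changed

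*SAP*

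**What the plan says.** Iron metabolism is among the secondary pharmacodynamic effects in SAP section 2. Ferritin appears in three planned summaries:

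- **By visit (SAP 5.7.2.5).** Observed values, absolute change and percentage change are given at each post-baseline visit. After Screening and Cycle 1 Day 1, iron parameters are drawn on "Day 1 and Day 8 of Cycle 2, Day 1 of Cycle 3, 4, and 5, EOT, PTFU and EOS visits".
- **Shift (SAP 5.7.2.5).** "Shift analyses will also be performed to summarize serum ferritin EOT change from baseline". Three categories are promised, with cut points at 300 for males, 150 for females, and 1000 µg/L.
- **Maximum (SAP 5.7.2.9).** "Maximum percentage decrease in serum ferritin", summarised by mean, median and range per dose cohort. No visit, time window or confirmation rule is attached.

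Baseline for ferritin is one value (SAP 5.1): "For all other parameters, baseline is defined as the last observation on or prior to Cycle 1 Day 1".

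On chelation, Protocol 9.3.2 excludes "Iron chelation therapy if initiated within 56 days prior to Cycle 1 Day 1", and Protocol 10.2.1 says "Iron chelation therapy is allowed unless initiated within 56 days prior to C1D1". The SAP lists "Baseline iron chelation therapy" among the baseline characteristics (5.4) and lists concomitant medications per patient (5.6.1). Chelation is absent from the ferritin analyses in 5.7.2.5 and 5.7.2.9 and from the subgroup factors in 5.7.3.3.

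**The concern.** Two separate mechanisms can produce a ferritin fall that is not a drug effect.

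The first is chelation, which is given to lower iron. Patients already on it for at least 56 days can enrol, and their ferritin may still be falling. A patient who starts or changes a chelator on study would contribute later values to the same row as everyone else. For hemoglobin, the SAP removes a known confounder by excluding values within 7 days after a transfusion (5.7). Ferritin has no comparable rule.

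The second is selection. Taking the lowest of several noisy values against one noisy value gives a decrease on average even when nothing has happened. The size grows with the number of draws, so it is larger in completers than in early dropouts, and cohorts with different dropout are not comparable. There is no control arm in which to see the same artefact.

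At stake is how a stated secondary effect is read. No test or decision rule depends on ferritin, and the primary endpoint is untouched.

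**Working it through.** The documents give no ferritin effect size, variability or sample size, so there is no figure of the plan's own to reproduce.

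**Inputs from the documents**
- Post-baseline draws: Cycle 2 Day 1, Cycle 2 Day 8, Cycle 3 Day 1, Cycle 4 Day 1, Cycle 5 Day 1, EOT, PTFU and EOS (Days 22, 29, 43, 64, 85, 113, 141 and 169), so k = 8.
- SAP 5.7 states that "all efficacy endpoints will be derived based on the last dose + 56 days or the last date from transfusion record data", whichever is earlier. With a last dose on Day 85, 85 + 56 = Day 141. If this applied to ferritin, EOS (Day 169) would drop out and k = 7. The lead-in limits these rules to hemoglobin and transfusion endpoints, so k = 8 is the more natural reading. Through EOT only, k = 6.
- Baseline: one value.

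**Assumptions (not in the documents)**
- Within-patient CV of 10%, 20% or 30%, with draws independent or with lag-1 correlation 0.5.
- For chelation, 10-50% of patients chelated and a chelator-driven fall of 10-30% by Day 113.

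**Step 1: chance of any decrease, no true change.** If the baseline and k later values are exchangeable, the baseline is the lowest of the k + 1 values with probability 1/(k + 1). So P(maximum decrease > 0) = k/(k + 1), whatever the CV:
- k = 8: 8/9 = 88.9%
- k = 7: 7/8 = 87.5%
- k = 6: 6/7 = 85.7%
- k = 2 (early dropout): 2/3 = 66.7%
- k = 1 (one fixed visit): 1/2 = 50%

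**Step 2: mean size, no true change.** Simulation of 400,000 patients with lognormal ferritin at a constant true level. The statistic is the maximum over j of 100 × (1 − X_j/X_0).

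| Draws | Correlation | CV 10% | CV 20% | CV 30% |
|---|---|---|---|---|
| 8 | 0 | 12.6% | 22.5% | 30.2% |
| 8 | 0.5 | 11.0% | 19.8% | 26.7% |
| 7 | 0 | 12.0% | 21.4% | 28.7% |
| 7 | 0.5 | 10.3% | 18.5% | 25.0% |
| 6 | 0 | 11.3% | 20.0% | 26.8% |

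If true ferritin instead rises 20% by Day 113 (k = 8, independent draws), the mean maximum decrease is still 3.8%, 13.3% and 21.3%. The statistic can point the wrong way.

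**Step 3: one fixed visit instead.** With no true change, the median percentage change is 0% at every CV. The arithmetic mean percentage change is +1%, +4% and +9% at CV 10%, 20% and 30% (independent draws), because a ratio to a noisy baseline is skewed upward. A median or log-ratio avoids this.

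**Step 4: chelation.** A share f of patients with a chelator-driven fall d shifts the mean change by about f × d:
- Low end: 0.10 × 10% = 1 point.
- High end: 0.50 × 30% = 15 points.
- Middle case: 0.30 × 20% = 6 points. Simulated at CV 20%, this moves the median EOT change from 0% to −6.3% and the mean maximum decrease from 22.5% to 26.0%.
- In an escalation cohort, one patient with a 30% fall moves the mean by 30/3 = 10 points (3 patients) or 30/6 = 5 points (6 patients).

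**Step 5: is an on-study start permitted?** Protocol 9.3.2 and 10.2.1 restrict only initiation in the 56 days before Cycle 1 Day 1. Protocol 10.2 speaks of stable doses for chronic conditions. Its discontinuation rule covers new medications that the eligibility criteria specifically exclude, and the chelation exclusion is limited to the time before dosing. No section states an on-study rule outright.

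**Step 6: shift categories.** Both sides of the 1000 cut point include equality, so a value of exactly 1000 µg/L belongs to two categories. The text does not say whether the cut points form one three-level scale or separate two-way splits.

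**The case against.** The strongest reply is that the unbiased analysis is already planned. SAP 5.7.2.5 gives percentage change at every visit, including Cycle 5 Day 1 and EOT, with plots over time. A flat by-visit table beside a 25% maximum decrease would expose the artefact. A reader might infer that the planned tables cannot reveal the selection effect, or that every ferritin summary is a best-of-8. Neither is so: the selection bias belongs to the one line in 5.7.2.9. What stands is that this line is biased toward benefit and adds nothing to the by-visit results.

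On chelation, recent starters are excluded, baseline use is tabulated, and medications and laboratory values are listed, so an individual start can be traced. SAP 5.7 also presents efficacy summaries for low and high transfusion burden separately. All of this stands, but none of it separates chelated from unchelated patients in a ferritin summary. A reader might also infer that the protocol expressly lets patients start a chelator on study. It does not say so: that reading rests on silence, and the stable-dose wording leaves it ambiguous.

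The magnitudes rest on assumed values, and positive correlation between draws lowers them. That is correct. The direction of the maximum's bias does not depend on the CV.

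A reader might take all the shift categories to overlap, since 300 and above contains 1000 and above. Read as separate two-way splits, that is no defect, and only the value 1000 is double-counted.

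Finally, chelation groups would be nearly empty in cohorts of 3-6 patients, and dropping values after a chelator start creates informative missingness. Both points stand and shape the fix.

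**Conclusion.** The point holds as a modest, inexpensive correction to secondary, descriptive analyses.

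- The maximum percentage decrease should not be presented as a ferritin effect. With no true change, 8/9 of patients with all 8 draws show a decrease (exchangeability assumed). The mean is about 11-13%, 20-23% and 27-30% at assumed CVs of 10%, 20% and 30%. It is slightly lower with 7 draws and smaller again in patients with fewer.
- Chelation-driven and drug-driven falls cannot be separated in any planned ferritin summary, only through listings. The possible shift of 1 to 15 points is illustrative, because the documents give neither the share of patients chelated nor the size of a chelator effect.
- The shift categories have one definite error, at 1000 µg/L, and one ambiguity of structure.

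A reader might go further and conclude that any ferritin benefit from this trial would be spurious. The documents do not support that: the by-visit changes are free of the selection effect, and how far chelation matters depends on data not yet tabulated. The SAP is written against protocol amendment 06, whereas the protocol reviewed has no expansion cohort 3, so the chelation wording should be confirmed in that amendment.

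**What to change.** Amend the SAP as follows.

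1. **Chelation (5.7.2.5).** Add ferritin summaries by chelation status: none; stable since before baseline; started or changed on study. Present them mainly in the expansion cohorts and pooled groups, since escalation cohorts have 3-6 patients. Add a sensitivity analysis that excludes values after an on-study start or change. Keep it as a sensitivity analysis, because the excluded values are not missing at random.
2. **Maximum (5.7.2.9).** Delete the maximum percentage decrease. Name the percentage change at Cycle 5 Day 1 and EOT, already planned in 5.7.2.5, as the ferritin effect summary, preferably as a median or log-ratio.
3. **Shift table (5.7.2.5).** Assign 1000 µg/L to one category only, and state whether the cut points are separate two-way splits or one three-level scale.

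The protocol sections on concomitant medication and chelation should also be reconciled, so that the on-study position is stated rather than inferred.

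The cost is SAP wording and some programming. Baseline chelation and concomitant medications are already collected. The downside is smaller groups per row.
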